#### APPENDIX B1, 2 & 3 Participant Information Sheet; Consent Form; Usability Assessment Form

#### APPENDIX B1 Participant Information Sheet

see separate documentation

APPENDIX B2 Consent Form

see separate documentation

APPENDIX B3 Usability Assessment Form

see separate documentation

#### APPENDIX C1&2

#### Items for List of Cases and Abbreviated List of Cases

APPENDIX C1 List of Cases at NHS site

Hospital number

Participant-lesion number

#### Diagnostic category (histopathology)

1 not melanoma

2.1 melanoma-in-situ (including lentigo maligna and acral lentiginous melanoma-in-situ)

- 2.2 melanoma superficial spreading
- 2.3 nodular melanoma
- 2.4 lentigo maligna melanoma
- 2.5 acral lentiginous melanoma
- 2.6 melanoma indeterminate
- 2.7 melanoma not otherwise defined
- 3 uncertain diagnosis
- 9 no information available/no biopsy

APPENDIX C2 Abbreviated List of Cases transferred to Medical Statistics, University of Aberdeen

Participant-lesion number

Diagnostic category (histopathology)

- 1 not melanoma
- 2.1 melanoma-in-situ (including lentigo maligna and acral
- lentiginous melanoma-in-situ)
  - 2.2 melanoma superficial spreading
  - 2.3 nodular melanoma
  - 2.4 lentigo maligna melanoma
  - 2.5 acral lentiginous melanoma
  - 2.6 melanoma indeterminate
  - 2.7 melanoma not otherwise defined
  - 3 uncertain diagnosis
  - 9 no information available/no biopsy

nomela® test result.//

#### APPENDIX D1&2 Data handling and governance

APPENDIX D1

#### Statement by Moletest (Scotland) Ltd. on Data Handling (2019b\_C8)

Please see Appendix D1 (2019b) submitted separately

		per participant			
step	activity	in secondary care			
		lesion 1	(lesion2 if present)	(lesion3 if present)	
	visit	1	1	1	
1	inclusion criteria	*	*	*	
1	exclusions	*	*	*	
2	Participant Information Sheet	*			
3	Consent Form	*			
4	nomela® test (1 - 3 minutes per lesion)	*	*	*	
5	check test is uploaded	*	*	*	
6	check receipt of email (e-consent/hospital number/participant number)	*	*	*	
7	search histology diagnosis (pathology/ dermatology) by EPR/ paper records	*	*	*	
8	add histology diagnosis to database (see Appendix C1&C2)	*	*	*	
9	confirm Abbreviated List of Cases (see Appendix C1&C2)	*	*	*	

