#### 4.2.5 The nomela® test result

The nomela® software recognises the perimeter of the lesion from the close-up cropped image. Using non-scalar metrics of the image within the recognised perimeter and a combination algorithm of 5 predefined parameters a score is obtained. Based on the score the nomela® test assigns the lesion either to "no evidence of melanoma" (group N) or to "melanoma not excluded" (group R). Both groups contain benign lesions but group N should contain no melanomata.

All information from the test is transferred automatically to the Study Log. Completion of the nomela® test is normally shown on the device by a Result page. For this Study the result will not be available to the operator and research team but will be passed to the medical statisticians.

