### 4.3 Clinical data collection

#### 4.3.1 Clinical data collection

The Study nomela® C8 is designed to eliminate paper case record forms and paper participant log. The nomela® test is electronic and is designed to eliminate transcription errors: the Patient(Participant) information, as hospital number, is captured by scanning at the start of the nomela® test. A cumulative Study database is populated automatically in a secure system. This information (except for the Result) is available to the authorised specialists and clinical research team accessible by approved systems.

(see 4.2.3)

(see Statement on the handling of Data, Appendix D) The (only) further information required for the Study is the histopathology diagnosis. This information is obtained from the Dept of Histopathology/ EPR by category by authorised personnel from Clinical Research/ Dermatology/Pathology requiring manual entry to the Study database. (see 4.3.4)

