4.3.5 Case Lists

List of Cases

The List of Cases generated from the Study database will show:

Participant-lesion number (maximum of 9 lesions per participant) Hospital number Diagnostic category (histopathology)

(see 4.3.4 and Appendix C1)

Abbreviated List of Cases

The Abbreviated List of Cases generated from the Study database will show:

Participant-lesion number

Diagnostic category (histopathology)

nomela® test result

forming the Study Database for statistical analysis for forwarding to the University of Aberdeen.

(see Appendix C2)

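### Appendix E step 9 calls for confirmation, within the secondary-care schedule, of a list that shows the nomela result; this is inconsistent with the masking in 4.2.4, 4.2.5 and 4.3.1

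*Protocol*

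**What the plan says.** The protocol masks the test result in three places. Section 4.2.4 keeps the Result and Report pages from the operator. Section 4.2.5 goes further: "For this Study the result will not be available to the operator and research team but will be passed to the medical statisticians". Section 4.3.1 applies the same rule to the database: "This information (except for the Result) is available to the authorised specialists and clinical research team".

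There are two case lists. Appendix C1, labelled as the list at the NHS site, holds hospital number, participant-lesion number and diagnostic category, with no result. The second list is introduced in 4.3.5 by "The Abbreviated List of Cases generated from the Study database will show", followed by participant-lesion number, diagnostic category and test result. Its purpose is given there as "forming the Study Database for statistical analysis for forwarding to the University of Aberdeen". Appendix C2 repeats its content, ending with "nomela® test result".

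The Schedule of Events in Appendix E is set out per participant and "in secondary care". Its last three steps, each marked for every lesion, are a search for the histology diagnosis (step 7), "add histology diagnosis to database (see Appendix C1&C2") (step 8) and "confirm Abbreviated List of Cases (see Appendix C1&C2") (step 9).

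**The concern.** Steps 1 to 8 cover eligibility, information, consent, testing, upload and email checks, and histology search and entry. Elsewhere the protocol gives testing and histology entry to site personnel (4.1.3, 4.3.1, 4.3.4). A reader working through the schedule would naturally treat step 9 as a site task too, and it names the list that carries the result.

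Two things would then be at stake.

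- **Diagnosis coding.** The histology category is entered by hand from a set of codes that includes uncertain (3) and no information (9). Under 5.0 a Case needs a histology-confirmed diagnosis of melanoma or not-melanoma, so a lesion coded 3 drops out of the analysis. Someone who sees a melanoma code beside a group N result could query or revise it, with no matching scrutiny of concordant lesions.
- **Later tests.** The operator crops each close-up image by hand (4.2.3) and lesions are judged for suitability (3.3). If results become known while recruitment continues, that knowledge could influence how later lesions are handled.

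**Working it through.** The protocol gives no figure to reproduce here. The check is one of consistency, followed by a short illustration.

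**Passages side by side**

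1. *Does the list in step 9 contain the result?* Yes, by 4.3.5 and again by Appendix C2.
2. *Is the result withheld from site staff?* Yes. 4.2.4 covers the operator, 4.2.5 the operator and research team, and 4.3.1 the authorised specialists and clinical research team.
3. *Is step 9 placed in a site schedule?* Yes. It sits under the secondary-care heading and is marked lesion by lesion, directly after histology entry.
4. *Does step 9 say who confirms, when, or whether the result column is hidden?* No.
5. *Can step 9 unmask the initial coding of the same lesion?* No. In the schedule's order the code is already in the database at step 8. What remains is later revision of that code. None of the sections compared here locks the code before the result is set beside it.
6. *Could step 9 fall within recruitment?* It could. Recruitment is planned for 6 months (3.6). Under 4.4.2.3 the hashed hospital number is removed if no histology is entered within 12 weeks of the test, so much of the histology entry must happen while recruitment is open. The pilot melanoma-rate rule (3.5) and the limit of 15 discordant melanomas (3.8) also need diagnoses before recruitment ends. Confirmation done in sequence, lesion by lesion, would therefore overlap recruitment. Confirmation done once at the end would not.

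Items 1 to 3 establish the inconsistency. Item 4 leaves open whether a breach would occur in practice. Items 5 and 6 bound the exposure.

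**Illustration of scale**

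Inputs: 200 confirmed melanomas (5.1), and 95% as the level in Objective 2. Sensitivity is taken here as the share of confirmed melanomas assigned to group R, in line with 1.4.3. The discordant counts and the numbers re-coded are assumptions.

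If d of 200 melanomas fall in group N and k of those are moved to category 3, sensitivity changes from (200 − d)/200 to (200 − d)/(200 − k).

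| d | k | Before | After |
|---|---|---|---|
| 10 | 3 | 190/200 = 95.0% | 190/197 = 96.4% |
| 10 | 5 | 190/200 = 95.0% | 190/195 = 97.4% |
| 12 | 3 | 188/200 = 94.0% | 188/197 = 95.4% |

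In the last row the estimate crosses 95% with a discordant count below the limit of 15 in 3.8. The rows show how few lesions matter. They do not predict what would happen.

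**The case against.** The strongest reply is that one unattributed schedule line should not be read as overriding three specific access rules. Step 9 names nobody. The table heading gives a setting and does not assign a task. Confirming a list may mean only checking that it is complete or has been generated. Appendix C2 is itself headed as the list sent to Medical Statistics at the University of Aberdeen. Step 8 carries the same loose reference to both appendices, so that reference does not prove that staff see the result column. The separate data-handling statement and information governance flow diagram, which are not to hand, may settle access. These points stand. A reader might infer that the masking is broken by the plan's own procedure; the documents do not support that.

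A reader might also infer that the same people crop images, enter codes and confirm results during recruitment. The protocol does not say so. The operator is a clinical research nurse, while histology may be entered by staff from Clinical Research, Dermatology or Pathology. Histology collection runs to 12 weeks after recruitment, and confirmation at that point could not affect any later test.

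Finally, the category comes from a routine pathology report, so re-coding a melanoma as uncertain would conflict with the source record, and nothing in the documents supports a re-coding rate of 3 or 5 in 10. That also stands, and it is why the percentages are illustration only.

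None of this removes the inconsistency. Express masking rules are exactly what a schedule step should not contradict, and the silence on actor, timing and content is the gap to close.

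**Conclusion.** The point holds as an inconsistency with a possible consequence. Step 9, placed in the secondary-care schedule, calls for confirmation per lesion of a list that by definition shows the nomela result beside the diagnosis. 4.2.4, 4.2.5 and 4.3.1 withhold that result from site staff. If site staff perform the step with the result visible, the masking is breached. It is not shown that they would, or that any bias would follow.

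The exposure is limited to revision of codes already entered and, only if confirmation runs during recruitment, to cropping and suitability judgements on later lesions. No expected size can be given. The shift from 95.0% to 96.4% or 97.4% rests on assumed discordant and re-coding counts and shows only that the primary estimate is sensitive to a handful of lesions. Because the correction is nearly free, it should be made before recruitment starts.

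**What to change.** In Appendix E, change step 9 so that the site confirms the List of Cases (Appendix C1: hospital number, participant-lesion number, diagnostic category, no result). In 4.3.5, state that the Abbreviated List with the result is generated from the database, is released only to the University of Aberdeen, and is released only after the histology codes in it have been confirmed and locked. Locking in batches would still allow the discordance count in 3.8 to be kept during the study.

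The cost is a few lines of wording. Both lists already exist, and the site can still check every linkage and diagnosis from C1.

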#### Mortality from malignant melanoma trends

Malignant melanoma is the 17th most common cause of cancer death in the UK (2014), accounting for 2% of all cancer deaths.

In 2014, there were 2,459 malignant melanoma deaths in the UK: 1,431 (58%) in males and 1,028 (42%) in females, giving a male:female ratio of around 14:10.The crude mortality rate shows 5 malignant melanoma deaths for every 100,000 males in the UK and 3 for every 100,000 females.

The European age-standardised mortality rates (AS rates) do not differ significantly between the constituent countries of the UK for either sex.

Malignant melanoma mortality rates have increased by 156% in the UK since the early 1970s.

The European Age-Standardised (AS) mortality rates between 1971-1973 and 2012-2014, increased for males by 237% and for females by 89% in this period.

AS mortality rates in the UK between 2003-2005 and 2012-2014 for malignant melanoma have increased by 15% for males and females combined, with a larger increase in males (20%) than in females (8%).

In England (2007-09), cutaneous melanoma age standardised incidence rates for males and females were 16.6|17 per 100,000 respectively. Tumour thickness data showed (2007-09) that in 45% of males | 53% of females tumours were thinner than 1mm (T1). Thicker tumours of 1.01-2mm (T2), 2.01-4mm (T3) and >4mm (T4) were observed in 22%, 19% and 14% of males, and 21%, 15% and 10% of females respectively. In addition 4% of cases under 50 years old were T4 compared with 14% of 50 years old and over.

Malignant Melanoma Standardised Mortality Rates (SMR) and Age Standardised Mortality Rates (aSMR) by Strategic Health Authorities in England showed a variation in mortality across England and between males and females. The average SMRs in England (2008-10) for males and females were 3.1 v 2.0 per 100,000 respectively.

The average aSMR per 100,000 population for malignant melanoma (England 2008-2010) in all 10 strategic health authorities was male 3.2 and female 2.05.

(drawn from Public Health England NCRAS ncin.org.uk (National Cancer Intelligence Network)
